In line with these recommendations, study 116945 [DTPA (BOOSTRIX)-047] will be conducted to evaluate the immunogenicity and safety of GlaxoSmithKline (GSK) Biologicals' dTpa vaccine, *Boostrix*, in pregnant women, *as well as the transfer of maternal antibodies against pertussis to the foetus (cord blood sample at delivery)*. Subjects will receive a dose of *Boostrix* during pregnancy or immediately post-delivery. (*Amended 06 September 2016*)

All infants born to pregnant women who participate in study 116945 [DTPA (BOOSTRIX)-047] will be offered enrolment in the present study. This study will be conducted to evaluate the immunogenicity and safety of GSK Biologicals' combined diphtheria-tetanus-acellular pertussis-hepatitis B-inactivated poliovirus and *Haemophilus influenzae* type b vaccine (DTPa-HBV-IPV/Hib), *Infanrix hexa*, given in the primary vaccination schedule. This will help us evaluate if the presence of transplacentally transferred maternal antibodies interfere with the immune response to primary vaccination with *Infanrix hexa* and a co-administered pneumococcal conjugate vaccine given as a part of this study in infants.

- Rationale for the study design

This phase IV study is a follow-up of the study 116945 [DTPA (BOOSTRIX)-047]. The immunogenicity and safety of *Infanrix hexa* when administered as a part of the primary vaccination schedule, *according to the routine national immunisation schedule (3 doses given at 2, 4 and 6 months of age or at 2, 3 and 4 months of age or 2 doses given at 3 and 5 months of age or at 2 and 4 months of age)* will be evaluated. *As part of the study*, subjects will also receive *Prevenar 13 according to the routine national immunisation schedule*. The immunogenicity and safety of the booster dose of the same vaccines in infants in the second year of their life will be assessed in another follow-up study DTPA (BOOSTRIX)-049. (*Amended 06 September 2016*)

This study will have two groups:

- dTpa Group: This group will consist of infants born to mothers belonging to the dTpa Group in study 116945 [DTPA (BOOSTRIX)-047] i.e. who received a single dose of *Boostrix* during pregnancy and a dose of placebo immediately post-delivery. All infants in this group will receive *Infanrix hexa* co-administered with *Prevenar 13* **according to the routine national immunisation schedule. (Amended 06 September 2016)**

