5.3. Method of blinding

This study will be conducted in an open-label manner since the treatment is similar between the two groups. Also, the data related to the study groups will be unblinded at the end of study 116945 [DTPA (BOOSTRIX)-047].

Note: The study personnel operating SBIR and the site staff will remain blinded towards the treatment allocation to subjects in study 116945 [DTPA (BOOSTRIX)-047].
(Amended 06 September 2016)

The laboratory in charge of the laboratory testing will be blinded to the treatment, and codes will be used to link the subject and study (without any link to the treatment attributed to the subject) to each sample.

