4. ENDPOINTS

4.1. Primary endpoints

- Immunogenicity with respect to components of *Infanrix hexa*.
 - Anti-diphtheria, anti-tetanus, anti-HBs, anti-poliovirus type 1, anti-poliovirus type 2, anti-poliovirus type 3 and anti-polyribosyl-ribitol phosphate (anti-PRP) seroprotection status, one month after the last dose of primary vaccination.

A seroprotected subject is a subject whose antibody concentration/titre is greater than or equal to the level defining clinical protection. The following seroprotection thresholds are applicable:

 - Anti-diphtheria antibody concentrations ≥ 0.1 IU/mL.
 - Anti-tetanus antibody concentrations ≥ 0.1 IU/mL.
 - Anti-HBs antibody concentrations ≥ 10 mIU/mL.
 - Anti-poliovirus types 1, 2 and 3 antibody titres ≥ 8 .
 - Anti-PRP antibody concentrations ≥ 0.15 $\mu\text{g/mL}$.
 - Vaccine response to PT, FHA and PRN antigens, one month after the last dose of primary vaccination.

Vaccine response to the PT, FHA and PRN antigens, is defined as:

- appearance of antibodies in subjects who were initially seronegative (i.e., with concentrations $<$ cut-off value).
- at least maintenance of pre-vaccination antibody concentrations in subjects who were initially seropositive (i.e., with concentrations \geq cut-off value).

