5.2.3. Elimination from ATP cohort for immunogenicity

5.2.3.1. Excluded subjects

All eliminations from the primary study 116945 [DTPA(BOOSTRIX)-047] will be applicable for this follow up study except for the visit specific elimination codes (2090, 2100 and 2120).

A subject will be excluded from the ATP cohort for immunogenicity when he/she is excluded from the ATP cohort for safety (see Section 5.1.3)

The following additional codes will be used:

Code	Decode => Condition under which the code is used
2010	
Protocol violation (inclusion/exclusion criteria) including age and excluding codes mentioned below.
 
A male or female between, 6 and 14 weeks of age (including 6 weeks and up to and including 14 weeks and 6 days of age) at the time of the first vaccination.
 
Healthy subjects as established by medical history and clinical examination before entering into the study.
 
This code is also inherited from the mother

2040	
Administration of any medication forbidden by the protocol=>
 
Immunosuppressants or other immune-modifying drugs administered chronically (i.e. more than 14 days) since birth. For corticosteroids, this will mean prednisone \geq 0.5 mg/kg/day, or equivalent. Inhaled and topical steroids are allowed.
 
Long-acting immune-modifying drugs administered at any time during the study period (e.g. infliximab).
 
This code is also inherited from the mother

2050	
Underlying medical condition forbidden by the protocol =>
 
Subjects may be eliminated from the ATP cohort for immunogenicity if, during the study, they incur a condition that has the capability of altering their immune response (e.g. any confirmed or suspected immunosuppressive or immunodeficient condition) or are confirmed to have an alteration of their initial immune status.

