2080	
Vaccination done but: noncompliance with vaccination schedules (dates of vaccination not corresponding to protocol intervals or unknown vaccination dates)
 
Intervals between study visits for subjects vaccinated with Infanrix hexa at 2, 4 and 6 months of age is 42-104 days from birth to visit 1, 52-78 days from visit 1 to visit 2, 52-78 days from visit 2 to visit 3.
 
Intervals between study visits for subjects vaccinated with Infanrix hexa at 2, 3 and 4 months of age is 42-104 days from birth to visit 1, 21-48 days from visit 1 to visit 2, 21-48 days from visit 2 to visit 3.
 
Intervals between study visits for subjects vaccinated with Infanrix hexa at 2 and 4 months of age is 42 to 104 days from birth to visit 1, 52-78 days from visit 1 to visit 2.
 
Intervals between study visits for subjects vaccinated with Infanrix hexa at 3 and 5 months of age is 42 to 104 days from birth to visit 1, 52-78 days from visit 1 to visit 2.

2090	
Blood sample taken but: noncompliance with blood sampling schedules (dates of blood sampling not corresponding to adapted protocol intervals or unknown blood sample/vaccination dates) => 21-48 days from last vaccination visit to visit 4

2100	
Serological results not available for antigens POST vaccination (including lost samples, blood sample not done, unable to test, absence of parallelism) => no immunogenicity results available at visit 4.

2120	
Obvious incoherence, abnormal serology evolution or error in data (incoherence between CRF and results, wrong sample labelling)

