6.3. Immunogenicity

6.3.1. Analysis of immunogenicity planned in the protocol

The primary analysis will be based on the ATP cohort for analysis of immunogenicity. If in any vaccine group, the percentage of enrolled subjects excluded from this ATP cohort is more than 5%, a second analysis based on the TVC will be performed to complement the ATP analysis. All analyses will be descriptive. For each group, at each timepoint that a blood sample result is available:

- Seropositivity rates against PT, FHA and PRN antigens and pneumococcal antigens (1, 3, 4, 5, 6A, 6B, 7F, 9V, 14, 18C, 19A, 19F, 23F) with exact 95% CI [Clopper, 1934] will be calculated.
- Seroprotection rates against diphtheria toxoid, tetanus toxoid, HBs, PRP antigen and poliovirus types 1, 2, 3 antigens (with exact 95% CI [Clopper, 1934]) will be calculated.
- Percentage of subjects with anti-pneumococcal serotypes (1, 3, 4, 5, 6A, 6B, 7F, 9V, 14, 18C, 19A, 19F, 23F) antibody concentrations, depending on the GSK laboratory or WHO reference laboratory assay cut-offs, will be calculated along with its exact 95% CI [Clopper, 1934].
- Percentage of subjects with anti-D and anti-T antibody concentrations ≥ 1.0 IU/mL will be calculated along with its exact 95% CI [Clopper, 1934].
- Percentage of subjects with anti-PRP antibody concentrations ≥ 1.0 $\mu\text{g/mL}$ and anti-HBs antibody concentrations ≥ 100 mIU/mL will be calculated along with its exact 95% CI [Clopper, 1934].
- GMC/GMT with 95% CI will be tabulated for antibodies against each antigen.

For serology results one month after last vaccination dose:

- The vaccine response rates to PT, FHA and PRN (with exact 95% CI) will be calculated.
- The distribution of antibody concentrations/titres for each antigen will be displayed using reverse cumulative distribution curves (RCCs).
- The distribution of antibody concentrations or titres of each antigen will be tabulated.

Additional summaries will be provided based on country.

Handling of missing data:

For a given subject and a given immunogenicity measurement, missing or non-evaluable measurements will not be replaced. Therefore, an analysis will exclude subjects with missing or non-evaluable measurements.

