Total = subjects either seropositive or ser1gative at pre-vaccination

Vaccine response to PT, FHA and PRN antigens is defined as:

For subjects with pre-vaccination antibody concentration below the assay cut-off, post-vaccination antibody concentration equal or above the assay cut-off,

For subjects with pre-vaccination antibody concentration equal or above the assay cut-off, post-vaccination antibody concentration equal or above the pre-vaccination antibody concentration

N = number of subjects with pre- and post-vaccination results available

[figure not shown]
n(%) = number(percentage) of subjects with booster response

95% CI = 95% confidence interval; LL = Lower Limit, UL = Upper Limit

*Pre-Pri = blood sample to be collected before the first dose of the primary vaccination course

Note: The assay cut-off is 2.693 IU/mL for anti-PT, 2.046 IU/mL for anti-FHA, and 2.187 IU/mL for anti-PRN.

Template 14 Reverse cumulative curve for anti-diphtheria antibody concentration before first dose and 1 month post last dose of the primary vaccination course (ATP cohort for immunogenicity)

dTpa Group = This group will consist of infants born to mothers belonging to the dTpa Group in study 116945 [DTPA (BOOSTRIX)-047]. All subjects in this group will receive *Infanrix hexa* co-administered with *Prevenar 13* according to the routine national immunisation schedule.

Control Group: This group will consist of infants born to mothers belonging to the Control group in study 116945 [DTPA (BOOSTRIX)-047]. All subjects in this group will receive *Infanrix hexa* co-administered with *Prevenar 13* according to the routine national immunisation schedule.

Pre-Pri = blood sample to be collected before the first dose of the primary vaccination course

Post-Pri = blood sample to be collected 1 month after the last dose of the primary vaccination course

Note: The groups shown in figure are indicative only. Actual groups may differ.

Template 15 Number and percentage of subjects who received study vaccine doses by vaccination group (Total vaccinated cohort)

Total number of doses received	dTpa group N =		Control group N =	
	n	%	n	%
0				
1				
2				
3				
Any				

dTpa Group = This group will consist of infants born to mothers belonging to the dTpa Group in study 116945 [DTPA (BOOSTRIX)-047]. All subjects in this group will receive *Infanrix hexa* co-administered with *Prevenar 13* according to the routine national immunisation schedule.

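### Exclusion code 2120 allows an infant to be dropped from the primary ATP cohort for an undefined abnormal course of serology, wording wide enough to cover a pertussis non-response, with no stated masking of the decision

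*SAP*

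**What the plan says.** SAP section 5.2.3.1 introduces its list with "The following additional codes will be used", and these codes add to the exclusions already made for the ATP safety cohort. Code 2120 reads "Obvious incoherence, abnormal serology evolution or error in data (incoherence between CRF and results, wrong sample labelling". It gives no antigen, direction, threshold or deciding role. It acts on the whole infant, so a flag raised on one antigen removes the infant from every ATP endpoint.

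SAP section 6.3.1 makes that cohort primary: "The primary analysis will be based on the ATP cohort for analysis of immunogenicity". If more than 5% of enrolled subjects in any group are excluded from it, a second analysis on the TVC is added.

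SAP section 4.1 defines pertussis vaccine response in initially seropositive infants as "at least maintenance of pre-vaccination antibody concentrations in subjects who were initially seropositive". Template 13 gives the same rule in operational form: "For subjects with pre-vaccination antibody concentration equal or above the assay cut-off, post-vaccination antibody concentration equal or above the pre-vaccination antibody concentration".

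On masking, Protocol section 5.3 makes the study open-label and says "the data related to the study groups will be unblinded at the end of study 116945". The same section keeps the staff who run the randomisation system, the site staff and the testing laboratory blinded. It does not mention whoever assigns elimination codes.

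**The concern.** The Protocol synopsis says the study should help to "evaluate if the presence of transplacentally transferred maternal antibodies interfere with the immune response to primary vaccination". It also reports that maternal dTpa gives high infant pertussis antibody before the first dose and slightly lower responses after the primary series. A fall from Pre-Pri to Post-Pri is therefore a plausible finding, more so in the dTpa group than in the Control group, and the primary pertussis endpoint counts it as a failure.

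An exclusion rule that turns on how the serology evolved, with no limit on what counts as abnormal, can catch the same infants. Any who were coded would leave both numerator and denominator as failures, so the ATP response rate could only rise, and it would rise more in the group with more falls. If the person deciding knew the mother's group, the choice could also depend on group, even without intent.

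Protocol section 10.4.3 has no criterion of this kind, and SAP section 9 does not list it as a change.

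**Working it through.** **1. The plan's own figures.** Protocol section 10.3 has no power calculation. Its design figures are the exact 95% intervals in Table 22, for n = 300, 272 and 238. The Clopper-Pearson interval reproduces all 37 rows to one decimal when the count is a whole number next to n × rate. Examples: 255/300 gives 80.4 to 88.8, 226/238 gives 91.4 to 97.4, and 238/238 gives 98.5 to 100.0. The sample sizes follow from 340 per group: 340 × 0.9 = 306 (the table uses 300), 340 × 0.8 = 272 and 340 × 0.7 = 238.

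**2. Where the code and the endpoint overlap.**

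| Primary endpoint | Depends on Pre-Pri? | Can a fall alone be a failure? |
|---|---|---|
| PT, FHA, PRN, initially seropositive | Yes: Post must be at least Pre | Yes, any fall |
| PT, FHA, PRN, initially seronegative | Only to define status | No: failure is staying below the cut-off |
| Diphtheria, tetanus | No: post-dose threshold | No |
| HBs, PRP, polio types 1 to 3 | No: post-dose threshold; no Pre-Pri assay in Protocol Table 12 | No |

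The overlap is confined to 3 of the 10 primary components, and within those to infants seropositive at Pre-Pri.

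**3. Size if falls are coded 2120.** With r responders among n evaluable infants and k non-responders removed, the rate goes from r/n to r/(n − k). The shift is (r/n) × k/(n − k). The values of n, r and k below are assumptions; n = 270 lies between the plan's 238 and 300.

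| Start | k = 2 | k = 5 | k = 10 |
|---|---|---|---|
| 243/270 = 90.0% (85.8 to 93.3) | 243/268 = 90.7%, +0.7 | 243/265 = 91.7%, +1.7 | 243/260 = 93.5% (89.7 to 96.1), +3.5 |
| 256/270 = 94.8% | 256/268 = 95.5%, +0.7 | 256/265 = 96.6%, +1.8 | 256/260 = 98.5% (96.1 to 99.6), +3.7 |

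Over n = 238, 272 and 300 with starting rates near 70%, 85% and 95%, the shift is 0.2 to 0.4 points for k = 1, 1.2 to 2.0 for k = 5 and 2.4 to 4.2 for k = 10. Beside the intervals in Table 22, five exclusions move the estimate by less than the half-width. Ten move it by about the half-width when the rate is 90% or more.

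**4. Whether the TVC analysis would run.** The trigger is more than 5% of enrolled subjects in a group: more than 17 of 340, or more than 15 of about 300 (the SAP section 6.3.2 table shows 601 infants; an equal split is assumed). Protocol section 10.3 expects a 10% to 30% reduction in evaluable subjects, that is 34 to 102 of 340. Some of that loss may occur before enrolment here. However, the ATP cohort also excludes infants born before 37 weeks and inherits most of the mother's elimination codes, so the trigger would very probably be met. Under SAP section 5.1.2 the TVC keeps any vaccinated infant with immunogenicity data, including one coded 2120.

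**The case against.** A reader might infer that falls in antibody would be removed and the interference signal hidden. The documents point the other way:

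- The code opens with obvious incoherence, and its only examples are mismatched records and mislabelled samples.
- No passage calls a fall abnormal. Protocol section 1.1 describes rapid decay of maternal antibody in infants.
- Template 13 has a separate row for initially seropositive infants within the ATP cohort. If every fall were coded 2120, that row would show 100% by construction.
- The note under Table 22 says lower response rates were included in case of immune interference, so such non-responders were meant to be kept and reported.
- SAP section 6.1.2 tabulates eliminations by group with reasons, and Template 5 has a row for this code, so uneven use would be visible.
- The TVC analysis would very probably be reported beside the ATP result.

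A reader might also infer that unblinded staff assign the code. The abbreviation list describes the elimination code type as internal to the sponsor, but neither document says who decides or when relative to the unblinding of the mothers' study. The gap is that no masking is stated.

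Most of this stands, and it limits the harm. It does not remove the defect. The examples illustrate the code without confining it. Tabulation discloses use afterwards without preventing it. The TVC result is complementary, and because it also restores infants excluded for other reasons, it does not isolate the effect of this code.

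**Conclusion.** The point holds as a drafting weakness in an outcome-dependent exclusion rule, and correcting it is a cheap improvement. Code 2120 permits, on an undefined ground, the exclusion of an infant whose serology pattern is itself a primary-endpoint failure for PT, FHA or PRN, and no masking of that decision is stated. The consequence is a possible upward bias in the primary ATP vaccine response rate, more likely in the dTpa group: under 1 point for one or two exclusions and about 2 to 4 points for five to ten.

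Those sizes assume that every excluded infant is a non-responder, and the counts are not taken from the documents. The figures in Template 5 are illustrative, since SAP section 12 says its templates were copied from recent studies; they are no evidence of how often the code is used. The analysis is descriptive, so no test or margin is affected.

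**What to change.** In the SAP section 5.2.3.1 code table:

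1. Limit code 2120 to a sample, labelling, assay or CRF error supported by evidence other than the direction of change, and drop the second ground as a reason in its own right.
2. State that a PT, FHA or PRN Post-Pri value below Pre-Pri is never sufficient by itself.
3. Require that 2120 codes be assigned and frozen by staff without access to the allocation in study 116945.

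The cost is a sentence or two in the SAP and a listing without group labels for the elimination review. The downside is that an occasional odd but unexplained result, such as an undocumented sample swap, would stay in the ATP cohort.

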6. STATISTICAL ANALYSES

Note that standard data derivation rule and stat methods are described in annex 1 (see Section 11) and will not be repeated below.

6.1. Demography

6.1.1. Analysis of demographics/baseline characteristics planned in the protocol

Demographic characteristics (age in weeks, race, height [cm], weight [kg], head circumference [cm], body mass index in [kg/m^2]), cohort description and withdrawal status will be summarised by group using descriptive statistics:

- Frequency tables will be generated for categorical variables such as race;
- Mean, median and standard deviation will be provided for continuous data such as age.

The distribution of subjects enrolled among the study sites will be tabulated as a whole and per group.

6.1.2. Additional considerations

Gender, country, schedule of vaccination will also be summarised by group using above mentioned descriptive statistics.

All demography summaries will be generated for the TVC. The summary of age, height, weight, head circumference, gender will also be provided for the ATP cohort for immunogenicity.

Number and reason for elimination from ATP cohorts will be tabulated by group.

Quartile 1 and quartile 3 will be provided for continuous data such as age in weeks, race, height [cm], weight [kg], head circumference [cm], body mass index in [kg/m^2].

6.2. Exposure.

6.2.1. Analysis of exposure planned in the protocol

NA

6.2.2. Additional considerations

The number of doses administered will be summarized by vaccine.

6.3. Immunogenicity

6.3.1. Analysis of immunogenicity planned in the protocol

The primary analysis will be based on the ATP cohort for analysis of immunogenicity. If in any vaccine group, the percentage of enrolled subjects excluded from this ATP cohort is more than 5%, a second analysis based on the TVC will be performed to complement the ATP analysis. All analyses will be descriptive. For each group, at each timepoint that a blood sample result is available:

- Seropositivity rates against PT, FHA and PRN antigens and pneumococcal antigens (1, 3, 4, 5, 6A, 6B, 7F, 9V, 14, 18C, 19A, 19F, 23F) with exact 95% CI [Clopper, 1934] will be calculated.
- Seroprotection rates against diphtheria toxoid, tetanus toxoid, HBs, PRP antigen and poliovirus types 1, 2, 3 antigens (with exact 95% CI [Clopper, 1934]) will be calculated.
- Percentage of subjects with anti-pneumococcal serotypes (1, 3, 4, 5, 6A, 6B, 7F, 9V, 14, 18C, 19A, 19F, 23F) antibody concentrations, depending on the GSK laboratory or WHO reference laboratory assay cut-offs, will be calculated along with its exact 95% CI [Clopper, 1934].
- Percentage of subjects with anti-D and anti-T antibody concentrations ≥ 1.0 IU/mL will be calculated along with its exact 95% CI [Clopper, 1934].
- Percentage of subjects with anti-PRP antibody concentrations ≥ 1.0 $\mu\text{g/mL}$ and anti-HBs antibody concentrations ≥ 100 mIU/mL will be calculated along with its exact 95% CI [Clopper, 1934].
- GMC/GMT with 95% CI will be tabulated for antibodies against each antigen.

For serology results one month after last vaccination dose:

- The vaccine response rates to PT, FHA and PRN (with exact 95% CI) will be calculated.
- The distribution of antibody concentrations/titres for each antigen will be displayed using reverse cumulative distribution curves (RCCs).
- The distribution of antibody concentrations or titres of each antigen will be tabulated.

Additional summaries will be provided based on country.

Handling of missing data:

For a given subject and a given immunogenicity measurement, missing or non-evaluable measurements will not be replaced. Therefore, an analysis will exclude subjects with missing or non-evaluable measurements.

